#### **6.5.5 Vital Signs**

The baseline value is the last measurement taken prior to the first IP administration.

Vital signs (systolic blood pressure [SBP], diastolic blood pressure [DBP], pulse, body temperature and weight) will be summarized using mean, standard deviation, minimum, maximum and median by dose level, phase, and overall. Additionally, a within-participant change will be calculated per visit as the post-baseline measurement minus the baseline measurement and summarized by visit.

Tables for potentially clinically significant vital signs will be generated using baseline value and highest post-baseline value for each participant.

The following criteria are defined as clinically significant for each parameter:

Vital Sign Variable	Criteria
SBP	$\geq 180$ mmHg AND $\geq 20$ mmHg change from baseline
DBP	$\geq 105$ mmHg AND $\geq 15$ mmHg change from baseline
Pulse Rate	$\geq 120$ bpm AND $\geq 15$ bpm change from baseline

Vital signs data will be displayed in listings.

### 6.5.6 Electrocardiograms (ECGs)

The three values of each ECG parameter within a time point from the central reviewer will be averaged to determine time-specific parameter for a participant and used in summaries.

ECG variables will be summarized using mean, standard deviation, minimum, maximum and median for each dose level, phase, and overall at each treatment visit and time point, including changes from baseline.

Number and percentage of participants with normal and abnormal results as assessed by central review for the overall interpretation will be tabulated by dose level, phase, and overall at each treatment visit and time point. A shift analysis table showing shift in overall ECG interpretation from baseline to each time point will be provided. The worst of the three overall ECG interpretations will be used as the time-specific overall ECG interpretation for a participant.

The QT interval corrected for heart rate by Fridericia's formula, QTcF, is defined as:  $QTc (F) = QT/(RR)^{0.33}$ , where RR interval is inversely proportional to heart rate (approximately RR = 60/heart rate).

The QTcF interval will be summarized using frequency tables for each treatment visit and time point for values of clinical importance using the range criteria below.

	QTc Interval Criteria Value (msec)	
	Cumulative Category	Interval Category
Normal	$\leq 450$	$\leq 450$
Borderline	$> 450$	$> 450$ to $\leq 480$
Prolonged	$> 480$	$> 480$ to $\leq 500$
Clinically significant	$> 500$	$> 500$

The QTcF interval will also be summarized by the frequencies of participants with a change from baseline of clinical importance using the criteria identified below. These summaries will be provided for each treatment visit and time point.

Variable	Change from Baseline	
	Cumulative Category	Interval Category
QTc Interval (msec)	$<0$	$<0$
	$\geq 0$	$\geq 0$ to $\leq 30$
	$> 30$	$> 30$ to $\leq 60$
	$> 60$	$> 60$

Number and percent of participants with 12 lead ECG abnormalities as well as number and percent of participants whose 12 lead ECG reading changed from normal at baseline to abnormal will be tabulated by dose level, phase, and overall at each treatment visit and time point.

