### **5.2.6 Safety Endpoint: Electrocardiogram (ECG)**

12-lead ECGs will be recorded in triplicate at the scheduled time points (at least 2 minutes apart per time point). Each ECG tracing will be taken 5 minutes apart. ECGs will be read at the site for clinical decision making and transmitted to a central reviewer. Data from the central reviewer will be used in summary presentations.

The routine 12-lead ECG results will be summarized by dose level and by time point.

Interpretations of routine 12-lead ECG results will be summarized by dose level and by time point.

12-lead ECG data interpretations and quantitative values will be listed.

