#### **6.5.4 Clinical Laboratory Evaluation**

The baseline visit is the last measurement taken prior to initial study IP administration.

Quantitative clinical laboratory variables, i.e., hematology, biochemistry, coagulation and urinalysis will be summarized using mean, standard deviation, minimum, maximum and median by phase and dose level at each visit. Additionally, a within-participant change will be calculated as the post-baseline measurement minus the baseline measurement and summarized in the same way.

The number and percentage of participants in relevant categories will be summarized for each dose level, phase, and overall at each visit.

Frequency tabulations of qualitative clinical laboratory variables (urinalysis) will be presented by dose level, phase, and overall at each visit.

Laboratory results will also be graded using NCI-CTCAE, where possible. NCI-CTCAE grade of laboratory evaluations will be summarized by number and percentage of participants for each visit. Shift tables of NCI-CTCAE grade change from baseline to worst post-baseline grade will also be presented.

Laboratory results will be listed.

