## **6.8    Additional Conventions**

### **6.8.1    Analysis Windows**

No visit window will be used; nominal visit date will be considered date of visit.

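### SAP 6.5.6 plans the QTcF limit categories only by treatment visit and time point, so no specified table counts the participants who ever crossed a limit

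*SAP*

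**What the plan says.** SAP 6.5.6 averages the three centrally read tracings at a time point and then plans two QTcF category tables.

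- **Absolute value** (limits of 450, 480 and 500 ms): "The QTcF interval will be summarized using frequency tables for each treatment visit and time point for values of clinical importance".
- **Change from baseline** (limits of 30 and 60 ms): "These summaries will be provided for each treatment visit and time point".

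The counts of ECG abnormalities use the same unit: they "will be tabulated by dose level, phase, and overall at each treatment visit and time point". There is also a table of the normal/abnormal reading: "A shift analysis table showing shift in overall ECG interpretation from baseline to each time point will be provided".

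SAP 5.2.6 is more general. "The routine 12-lead ECG results will be summarized by dose level and by time point", and the interpretations and quantitative values are to be listed. On visit assignment, SAP 6.8.1 says: "No visit window will be used; nominal visit date will be considered date of visit".

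Other threshold-based safety sections count once per participant. For laboratory grades (6.5.4): "Shift tables of NCI-CTCAE grade change from baseline to worst post-baseline grade will also be presented". For vital signs (6.5.5), the tables are built "using baseline value and highest post-baseline value for each participant". For liver tests (6.5.4.1), each participant's highest value in the investigational period is used.

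**The concern.** Crossing 500 ms, or rising by more than 60 ms, is something that happens to a participant. The safety question is how many participants it happened to at each dose. A set of rows, one per time point, answers a different question: how many were above the limit on that occasion. The same participant may appear in several rows, and different participants may each appear in one.

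The denominators also move. SAP 6.1 bases percentages on participants with non-missing data, and these become fewer as participants leave treatment.

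ECGs are a named component of the primary safety endpoint (SAP 2.1 and 5.2), and the SAP itself labels values above 500 ms clinically significant. Leaving the participant-level count unspecified also leaves open which ECGs would enter it.

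**Working it through.** The documents state no figure on this point, so there is none to reproduce. The check is a comparison of text followed by illustrations.

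**1. Is an any-time count specified elsewhere?** Neither the SAP nor the protocol mentions a worst post-baseline QTcF. The column headed cumulative category in SAP 6.5.6 nests limits (above 450 includes above 480); it does not accumulate over time. Overall in SAP 6.1 means across dose levels and phases, not across visits. Protocol 9.4.3.4.1 asks only for summaries by arm, dose level and time point.

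**2. What the rows determine.** Let c_j be the number above a limit at time point j, N the number of participants, and E the number ever above it at the tabulated time points. Then

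max(c_j) ≤ E ≤ min(N, Σ c_j).

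The rows fix E only when the two bounds meet, for example when every c_j is zero.

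**3. How many rows.** Post-baseline time points for a single-agent escalation participant, from the ECG row and footnote of protocol Table 1:

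- Cycle 1: day 1 post-dose, day 8, day 15 = 3
- Cycle 2: day 1 pre- and post-dose, day 8, day 15 = 4
- Cycles 3 to 6: day 1 pre- and post-dose, 4 × 2 = 8

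The total is 3 + 4 + 8 = 15, or 16 with the end-of-treatment ECG. Stopping after 4 cycles gives 3 + 4 + 4 = 11; after 2 cycles, 3 + 4 = 7.

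**4. Illustrations (assumed inputs).**

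- With N = 12 (the planned phase 1 size) and c_j = 1 at each of 16 time points, the lower bound is 1 and the upper bound is min(12, 16) = 12. E lies between 1/12 = 8% and 12/12 = 100%.
- Suppose 3 of 6 participants each exceed +60 ms once, at different time points, and all six complete 6 cycles. No row exceeds 1/6 = 17%, while the any-time figure is 3/6 = 50%.
- For an assumed chance p per reading and k independent readings, the any-time probability is 1 − (1 − p)^k:

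| k | p = 1% | p = 2% |
|---|---|---|
| 15 (6 cycles) | 1 − 0.99^15 = 14% | 1 − 0.98^15 = 26% |
| 11 (4 cycles) | 1 − 0.99^11 = 10% | 1 − 0.98^11 = 20% |
| 7 (2 cycles) | 1 − 0.99^7 = 7% | 1 − 0.98^7 = 13% |

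Independence is the extreme case. As readings within a participant become more alike, these figures fall toward p itself.

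**5. Which ECGs the rows cover.** Protocol Table 3 schedules ECGs 30, 60 and 90 days after the last dose. Read literally, the term treatment visit in SAP 6.5.6 leaves them out of the QTcF category tables, but the term is not defined. For unscheduled ECGs the SAP gives no rule; section 6.8.1 neither assigns them to a row nor excludes them.

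**The case against.** The strongest reply is that little is lost.

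- **The count can be recovered.** The ECG listing in SAP 5.2.6 contains the values. Protocol 2.3.1.1 reports 4 participants treated as of 06 May 2022, phase 1 was planned at about 12, and SAP section 1 records early termination. A hand count is easy. SAP 6.5.6 also reports maxima by time point. This stands, and it limits the importance of the point. A listing is still not a prespecified summary: someone must decide whether follow-up and unscheduled ECGs count.
- **Other tables may show the event.** A reader might infer that a prolongation seen only on a follow-up or unscheduled ECG would be in no table. The documents do not support that. The summary in 5.2.6 and the interpretation shift table are not limited to treatment visits. A clinically significant ECG finding is an adverse event (protocol 10.3.1). It is treatment-emergent up to 30 days after the last dose (SAP 5.2.3), and serious events are summarized to 90 days (SAP 6.5.2). These routes depend on clinical judgement or cover only the normal/abnormal reading, so none gives the count by QTcF limit.
- **Nothing is understated.** A reader might also infer that the tables understate the proportion with prolongation. They do not: they report frequencies by time point, labelled as such, and state no any-time proportion.
- **Unseen specifications and no named QT risk.** Table layouts are in separate specifications (SAP 6.1), which may already hold such a row. Protocol Table 6 lists no QT or cardiac concern for ASP0739. Both are fair and bear on priority. Neither changes what the SAP itself specifies.

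**Conclusion.** The point holds in a limited form. SAP 6.5.6 specifies the QTcF categories only by treatment visit and time point, so no specified table gives the number of participants who ever crossed a limit. This is out of line with 6.5.4, 6.5.4.1 and 6.5.5. No QTcF category table is clearly specified for the follow-up ECGs, which rests on a literal reading of treatment visit, or for unscheduled ECGs, on which the SAP is silent.

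The documents do not allow a size to be put on the effect. The 3-of-6 example and the 14% and 26% figures are illustrations that assume all 6 cycles are given, although cycles beyond the second require clinical benefit and cycles 5 and 6 require partial response or stable disease. The percentages also assume independent readings. In a small study that stopped early, with all values listed, the practical impact is modest. The change is still worth making, because the summary concerns a named component of the primary safety endpoint and costs almost nothing.

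**What to change.** Add to SAP 6.5.6 a worst post-baseline row in each of the two QTcF category tables. Count each participant once: by the highest post-baseline time-point mean QTcF in the first table, and by the largest post-baseline increase in the second. Take these over all post-baseline ECGs, stating explicitly that unscheduled, end-of-treatment and 30, 60 and 90-day safety follow-up ECGs are included. Present by dose level, phase and overall, and keep the by-time-point tables as support.

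The cost is a short addition to the SAP text and two extra rows of output, from data already collected. In reading the new rows, note that a participant with more ECGs has more chances to cross a limit.

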### **6.5.7    Pregnancies**

A detailed listing of all pregnancies will be provided.

### **6.5.8    Eastern Cooperative Oncology Group (ECOG) Performance Status**

Number and percent of participants for each category of the ECOG performance status at each assessment time will be provided. The change from baseline to EOT score will also be summarized. Negative change scores indicate an improvement. Positive change scores indicate a decline in performance.

ECOG will also be summarized using shift table from baseline to post-baseline score for each dose level, phase, and overall by visit.

## **6.6    Analysis of Pharmacokinetics**

Cellular DNA load and kinetic parameters of ASP0739 will be summarized by using descriptive statistics including n, mean, standard deviation, minimum, median, maximum, coefficient of variation (CV), geometric mean, and geometric CV. Spaghetti and mean time-course plots of cellular DNA load will be constructed.

### **6.6.1    Estimation of Pharmacokinetic Parameters**

Participants with sufficient cellular DNA samples will have kinetic parameter estimates for ASP0739 including calculation of AUC,  $C_{max}$ , and  $t_{max}$  for each cycle estimated by the pharmacokineticist using a non-compartmental analysis method in reference to Manual for Non-Compartmental Analysis of Pharmacokinetic Data from Studies using PhoenixTM® WinNonlin® (Certara, Saint Louis, Missouri, US) software version 6.4 or higher.

Exploratory analysis between pharmacokinetic parameters and clinical measures (e.g., efficacy or safety) may be performed.

Kinetic parameters will be plotted against dose to make an assessment of their relationship.

## **6.7    Analysis of Pharmacodynamics**

Immune cell phenotyping biomarkers will be summarized by change from baseline at each time point by both absolute number and percentage.

## **6.8    Additional Conventions**

### **6.8.1    Analysis Windows**

No visit window will be used; nominal visit date will be considered date of visit.

### 6.8.2 Imputation Rules for Incomplete Dates

Missing or partial start and stop dates of adverse events, concomitant medications, and new anti-cancer therapy will be imputed according to Astellas standards using the following algorithm:

- Imputation rules for partial or missing stop dates:
  - If the month and year are present, then impute as the last day of that month.
  - If only the year is present, impute as December 31 of that year.
  - If the stop date is entirely missing, assume the event or medication is ongoing.
- Imputation rules for partial or missing start dates:

Start Date		Stop Date						missing	
		Complete: yyyymmdd		Partial: yyyyymm		Partial: yyyy			
		< 1 st dose	≥ 1 st dose	< 1 st dose yyyyymm	≥ 1 st dose yyyyymm	< 1 st dose yyyy	≥ 1 st dose yyyy		
Partial: yyyyymm	= 1 st dose yyyyymm	2	1	2	1	n/a	1	1	
	≠ 1 st dose yyyyymm		2		2	2	2	2	
Partial: yyyy	= 1 st dose yyyy	3	1	3	1	n/a	1	1	
	≠ 1 st dose yyyy		3		3	3	3	3	
Missing		4	1	4	1	4	1	1	

1 = Impute as the date of first dose; 2 = Impute as the first of the month; 3 = Impute as January 1 of the year;  
4 = Impute as January 1 of the stop year

For survival and other time-to-event endpoints, missing or incomplete death date will be imputed as the earliest feasible date on or after the date last known to be alive as the examples shown in the table below.

Incomplete date of death or new anti-cancer therapy	Date Last Known to be Alive/Not Started New Treatment	Imputed Date
?? APR 2020	31 MAR 2020	01 APR 2020
14 ??? 2020	31 MAR 2020	14 APR 2020
?? ??? 2020	31 MAR 2020	31 MAR 2020
?? APR ????	31 MAR 2020	01 APR 2020
14 APR ????	31 MAR 2020	14 APR 2020
?? ??? ????	31 MAR 2020	31 MAR 2020

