**Table 3 PFS Definition**

PFS		
Situation	Date of Event or Censor	Outcome
No evaluable post-baseline imaging assessments, no death	Date of first dose (Day 1)	Censor
Participant did not receive new anti-cancer therapy (ACT):		
Radiographical progression documented per RECIST v1.1	Date of radiological disease progression	Event
No radiographical progression, but death recorded on eCRF	Date of death	Event
Neither radiographical progression nor death	Date of last disease assessment	Censor
Participant received new anti-cancer therapy (ACT):		
Radiographical progression documented per RECIST v1.1 after new ACT	Date of last radiological assessment before start of new anti-cancer therapy	Censor
Radiographical progression documented per RECIST v1.1 before new ACT	Date of radiological disease progression	Event
No radiographical progression before new ACT but death recorded	Date of last radiological assessment before start of new anti-cancer therapy	Censor
No radiographical disease progression nor death	Date of last radiological assessment before start of new anti-cancer therapy	Censor
Missed >=2 scheduled radiological assessments		
If radiographical progression or death occurs after missing 2 scheduled radiological assessments	Date of last radiological assessment before missing 2 scans	Censor

PFS = Date of Event or Censor – Date of First Dose +1

Missing 2 scheduled imaging assessments:

Missing 2 scheduled imaging assessments is defined as the gap between two imaging assessments as more than 140 days (2.5 times the scheduled imaging assessment interval (2.5 x 56 days)). Imaging assessments after first iUPD will be excluded in PFS derivation.

Note: Participant cannot be censored at “NE”. If NE is the only previous assessment, then PFS will be censored at Day 1.

To apply the cut-off date to PFS is to exclude those tumor assessments after cut-off date and anti-cancer therapy date after cut-off date in the analysis.

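### SAP 6.8.2 gives two imputation rules for the start of new anti-cancer therapy and does not say which one the time-to-event endpoints use

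*SAP*

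**What the plan says.** SAP 6.8.2 has two parts.

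**General algorithm.** It begins "Missing or partial start and stop dates of adverse events, concomitant medications, and new anti-cancer therapy will be imputed" and states no limit by purpose or endpoint. Its start-date grid uses four codes, the first two being "1 = Impute as the date of first dose; 2 = Impute as the first of the month". Codes 3 and 4 give 1 January of the start year and of the stop year. Code 1 applies when the stop date is missing, or on or after first dose, and the start date is one of:
- wholly missing;
- year-only, in the first-dose year;
- month and year, in the first-dose month.

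**Time-to-event rule.** It begins "For survival and other time-to-event endpoints, missing or incomplete death date will be imputed", and the date is "imputed as the earliest feasible date on or after the date last known to be alive". That sentence does not mention new therapy. The table below it does: its columns are headed "Incomplete date of death or new anti-cancer therapy" and "Date Last Known to be Alive/Not Started New Treatment".

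No sentence says which rule prevails for the start of new therapy.

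**Where the date is used.** SAP Tables 2 to 5 (iPFS, PFS, iDOR, DOR) all depend on it. In Table 3, progression or death after new therapy is censored at "Date of last radiological assessment before start of new anti-cancer therapy". A separate Day 1 row is written for "No evaluable post-baseline imaging assessments, no death". SAP 6.4.2.5 to 6.4.2.8 provide listings only for these four endpoints. Protocol 9.6 confines its exceptions to the no-imputation principle to adverse events and concomitant medications.

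**The concern.** New anti-cancer therapy follows study treatment, so dating its start to the first dose is implausible. For adverse events and concomitant medications such a default has a clear use: Protocol 9.6 says imputed dates serve to classify them as treatment-emergent or concomitant. A new-therapy date does a different job, because it decides whether a progression counts.

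If a code 1 date were fed into Tables 2 to 5, no post-baseline scan could precede new therapy. An observed progression would then be reported as censored, and a response duration could end before the response began. Because the first rule names new therapy outright and the second rule's sentence does not, a programmer could defend either.

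**Working it through.** No power or alpha figure bears on this point. The check is to apply both rules to the same incomplete dates and carry the results through the SAP tables.

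**1. Reproduce the SAP's examples.** Read the second rule as the earliest calendar date, on or after the last known date, that matches the known parts. With the SAP's last known date of 31 March 2020, its six examples give 1 April, 14 April, 31 March, 1 April, 14 April and 31 March 2020. All six match the SAP.

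**2. Compare the two rules.** Assumed: stop date missing; last known not on new therapy 31 March 2020.

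| First dose (assumed) | Recorded start | General algorithm | Time-to-event rule |
|---|---|---|---|
| 6 Jan 2020 | wholly missing | 6 Jan 2020 | 31 Mar 2020 |
| 6 Jan 2020 | 2020 | 6 Jan 2020 | 31 Mar 2020 |
| 6 Jan 2020 | Apr 2020 | 1 Apr 2020 | 1 Apr 2020 |
| 4 Nov 2019 | 2020 | 1 Jan 2020 | 31 Mar 2020 |

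The rules differ in three of the four rows, and the general algorithm reaches the first dose in two. The third code 1 pattern, a month-year start in the first-dose month, also gives the first dose. It is not tabulated because January 2020 would contradict a last known date of 31 March.

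**3. Carry the dates into PFS.** Assumed: first dose 10 January 2022, progression scan 7 March 2022, therapy start recorded as 2022 only, last known not on new therapy 31 March 2022. Table 3 defines PFS as event or censor date minus first dose date plus 1.

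- *General algorithm.* Therapy start becomes 10 January 2022, so progression falls after it and PFS is censored at the last scan before it. Only a screening scan qualifies. Screening runs from Day -28 to Day -1, so that scan lies between 13 December 2021 and 9 January 2022, and PFS lies between -28 + 1 = -27 and -1 + 1 = 0 days. It is Day 1 only if the no-evaluable-imaging row is used instead, although this participant has an evaluable scan.
- *Time-to-event rule.* Therapy start becomes 31 March 2022 and progression precedes it. PFS is an event at 56 + 1 = 57 days.

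The contrast depends on the last known date. Had it been 1 March 2022, the second rule would impute 1 March, before the progression scan, and would censor too. Had it been 7 March, the two dates would tie, which Table 3 does not address.

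**4. Carry the dates into DOR.** Table 5 counts from the first CR or PR. Suppose instead that 7 March 2022 is the first response, later confirmed and followed by progression. Under the general algorithm the censor date is no later than 9 January 2022, which is 57 days before the response, so DOR is at most -57 + 1 = -56 days.

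**The case against.** The strongest reply is that the specific rule displaces the general one. The second rule is introduced for time-to-event endpoints, and its table has a heading and a column made for new therapy. PFS, iPFS, DOR and iDOR are time-to-event endpoints. The general algorithm would still have work to do elsewhere, for example in the tabulation of new therapy in SAP 6.2.7. This stands: it is the more natural reading, and the harm arises only if a programmer departs from it. It does not close the gap, because the first rule names new therapy without limit and the second rule's sentence leaves it out.

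A reader might infer more than the documents support:
- *That PFS and iPFS would be censored at Day 1.* Read literally, the censor date is the screening scan. Day 1 needs a row written for a different situation.
- *That DOR would be censored at Day 1.* Table 5 has no such row. The only Day 1 text for response duration is the note under Table 4 on non-evaluable assessments, which does not cover this case.
- *That every incomplete therapy date goes to first dose.* Only the code 1 cells do so, and a month-year start in a later month gives the same date under both rules.
- *That a planned estimate is damaged.* The study ended early (SAP Section 1). This SAP lists these endpoints without a Kaplan-Meier summary, and its response-rate sections state no rule based on the new-therapy date.

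**Conclusion.** The point holds as a drafting conflict with a narrow effect. SAP 6.8.2 states two rules for one date, they disagree for common patterns of missingness, and precedence is not stated. One of the stated rules gives an implausible start date.

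For an affected participant, the wrong choice turns a PFS or iPFS event into a censored value at zero or negative time (or Day 1), and could make DOR or iDOR negative. The 57-day illustration rests on assumed dates, including a last known date later than the progression scan. Across the study the effect is limited to individual listing values, although those listings are the only output SAP 6.4.2 plans for these endpoints. The documents do not say how many therapy start dates are incomplete, so the number affected cannot be given and may be zero.

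**What to change.** Make two edits in SAP 6.8.2 before database lock:

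1. Remove new anti-cancer therapy start dates from the general algorithm, or state that the algorithm does not apply to them for time-to-event endpoints. Stop-date imputation can stay if it is wanted for other displays.
2. In the sentence beginning "For survival and other time-to-event endpoints, missing or incomplete death date will be imputed", name the new-therapy start date beside the death date, and extend the anchor from the date last known alive to the date last known not to have started new treatment. This brings the sentence into line with the table's own headings, "Incomplete date of death or new anti-cancer therapy" and "Date Last Known to be Alive/Not Started New Treatment".

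The cost is two lines of text. No new data are needed and no other table has to change.
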